9.5.1.4 SF-36 physical component summary score

For patients who have died, the SF-36 PCS score after the death will be imputed as zero. For patients who permanently discontinue from study treatment, values collected after permanent discontinuation will generally be included in the analysis.

The changes from baseline in SF-36 PCS score will be analyzed using a MMRM model, in which, the response variable will be the changes from baseline in SF-36 physical component summary score; stratum (defined by prior ACEi/ARB medication usage [ACEi, ARB, None]), region, treatment (LCZ696, individualized medical therapy), visit and treatment-by-visit interaction will be included as fixed-effect factors; baseline SF-36 physical component summary score (BPSS), BSBP, stratum-by-BPSS, stratum-by-BSBP and visit-by-BPSS interactions will be included as covariates; the within-patient covariance will be modeled using an unstructured covariance matrix (a common matrix for the two treatment groups). The analysis will include all post-baseline scheduled visits up to Week 24 (Week 16 and Week 24) and will be performed based on the likelihood method with an assumption of MAR for missing data (other than due to death).

Based on the MMRM model, the estimates and the two-sided 95% confidence intervals will be provided for the adjusted means for the change from baseline in SF-36 PCS score at Week 24 in each of the two treatment groups (LCZ696 and individualized medical therapy), and for the adjusted mean difference (LCZ696 minus individualized medical therapy) at Week 24.

In addition, the SF-36 PCS score will be summarized by visit and treatment group using n, mean, standard deviation, min, Q1, median, Q3 max.

The FAS will be used for the above analyses.

9.5.1.5 SF-36 mental component summary score

The same analyses as SF-36 PCS score will also be performed for SF-36 MCS score, except that the BPSS in the models will be replaced by baseline SF-36 MCS score (BMSS), stratum-by-BPSS and visit-by-BPSS interactions in the analysis models will be replaced by stratum-by-BMSS and visit-by-BMSS interactions.

The FAS will be used for the above analyses.

9.5.1.6 Missing data handling in the secondary endpoint analyses

In the analyses described in Sections 9.5.1.1 to 9.5.1.5, death is considered the worst possible outcome and hence scheduled visits after death will be imputed accordingly. Other missing data is assumed to be MAR.

As a sensitivity analysis, the controlled multiple imputation approach based on pattern mixture models will be applied (Carpenter and Kenward 2013), whereby all missing data of patients in the LCZ696 group who permanently discontinue study treatment due to: adverse events or lack of efficacy, will be assumed to behave like patients in the control group (individualized medical therapy) after permanent discontinuation and will be imputed based on the data from patients in the control group (individualized medical therapy) according to the stratum (defined by prior ACEi/ARB medication usage [ACEi, ARB, None]).

All other missing data will be considered as MAR within each arm and will be imputed using a multiple imputation approach (Carpenter and Kenward 2013) based on observed data within each arm according to the stratum. Of note, patients who permanently discontinue study treatment, are not considered discontinued from the study. It is planned to continue to collect and use data at scheduled visits even after permanent discontinuation of study treatment.

Furthermore, the missing data patterns in the secondary endpoint variables will be explored via by-treatment-group box plots or bar plots as appropriate for patients who permanently discontinue from study treatment due to adverse events or lack of efficacy, for patients who permanently discontinue study treatment due to any other reasons, for patients who did not permanently discontinue study treatment and for patients who take open label LCZ696 after permanent discontinuation from study treatment.

As additional supportive analyses, the main analyses for the secondary endpoints described in Sections 9.5.1.1 to 9.5.1.5 will be performed for the following data.

- Data where the responses after the death were set to missing for patients who died.
- Data where the LOCF approach was performed for missing data.
- Data where the responses after the first dose of open-label RASi or open-label LCZ696 after permanent discontinuation of study treatment will be set to missing and considered MAR. (This is called on-treatment analysis.)

9.5.1.7 Subgroup analyses

Subgroup analyses will be performed utilizing the corresponding analysis model used for primary and secondary endpoints, after adding the factors of subgroup and subgroup-treatment interaction to the model, to assess the consistency of the treatment effects across key clinically relevant subgroups listed below. The estimated treatment effect, two-sided 95% confidence interval, and the interaction p-value will be provided for each of the subgroups.

- Stratum (defined by prior ACEi/ARB medication usage [ACEi, ARB, None])
- Age group (< 65 years, ≥ 65 years; < 75 years, ≥ 75 years)
- Sex
- Region
- Baseline NYHA (Class I-II, Class III-IV)

- Diabetes (Yes [history of diabetes mellitus or HbA1c at screening \geq 6.5%], No[no history of diabetes mellitus and HbA1c at screening $<$ 6.5%])

9.5.2 Safety variables

The safety and tolerability assessments are listed below:

- Identified and potential risks (including angioedema, hyperkalemia, hypotension, renal dysfunction, liver)
- AEs and SAEs
- Sitting systolic, diastolic BP, and pulse pressure
- Heart rate
- Symptomatic hypotension
- Angioedema
- Hyperkalemia
- Renal dysfunction
- Other relevant laboratory values
- ECG changes

The assessment of safety will be based primarily on the frequencies of AEs, SAEs, and laboratory abnormalities. Other safety data will be summarized as appropriate.

The incidence of treatment-emergent AEs (new or worsened) will be summarized by primary system organ class, preferred term, severity, and relationship to study drug. In addition, the incidence of death, SAEs, and AEs leading to discontinuation will be summarized separately by primary system organ class and preferred term.

The incidence of AEs related to the identified and potential risks will be summarized by SMQ preferred terms.

Laboratory data will be summarized by presenting shift tables using extended normal ranges (baseline to most extreme post-baseline value), by presenting summary statistics of raw data and change from baseline values (mean, medians, standard deviations, ranges) and by the flagging of notable values in data listings. LFT categorical analysis will also be provided.

Data from other tests (eg ECG or vital signs) will be listed, notable values will be flagged, and any other information collected will be listed as appropriate.

Safety analyses will be performed based on the SAF. There will be no formal statistical inference analysis.

9.6 Analysis of exploratory variables

9.6.1 NT-proBNP up to Week 24

The changes from baseline in log(NT-proBNP) will be analyzed using a MMRM model, in which, the response variable will be the changes from baseline in log-transformed NT-proBNP; stratum (defined by prior ACEi/ARB medication usage [ACEi, ARB, None]), region, treatment (LCZ696, individualized medical therapy), visit and treatment-by-visit interaction will be

included as fixed-effect factors; baseline log-transformed NT-proBNP, stratum-by-baseline and visit-by-baseline interactions will be included as covariates; the within-patient covariance will be modeled using an unstructured covariance matrix (a common matrix for the two treatment groups). If the model fitting procedure does not converge, the AR(1) covariance structure will be used. The analysis will include all post-baseline scheduled visits up to Week 24 (Week 4, Week 12 and Week 24) and will be performed based on the likelihood method with an assumption of MAR for missing data.

Based on the MMRM model, the estimates and the two-sided 95% confidence intervals will be provided for the adjusted geometric means for the ratio of NT-proBNP over baseline NT-proBNP in each of the two treatment groups (LCZ696 and individualized medical therapy) at Week 24; and for the adjusted geometric mean ratio (LCZ696 over individualized medical therapy) at Week 24.

The FAS will be used for the above analyses

9.6.2 Estimated glomerular filtration rate (eGFR)

For the rate change in eGFR, the eGFR slope will be estimated from a mixed model, in which, the response variable will be the eGFR; stratum (defined by prior ACEi/ARB medication usage [ACEi, ARB, None]), region, and treatment (LCZ696, individualized medical therapy) will be included as fixed-effect factors; time (in month) and treatment-by-time interaction will be included as covariates; a patient level random intercept and a patient level random slope (time) will be included as random effects with a unstructured covariance matrix (a common matrix for the two treatment groups). Here, the time is computed as (date of assessment – date of randomization + 1)/30.4375. The analysis will include all assessments from central lab at all visits up to Week 24 (Baseline to Week 24, scheduled or unscheduled) and will be performed based on the likelihood method with an assumption of MAR for missing data.

Based on the mixed model, the estimates and the two-sided 95% confidence intervals will be provided for the adjusted mean slope in each of the two treatment groups (LCZ696 and individualized medical therapy), and for the adjusted mean difference (LCZ696 minus individualized medical therapy).

In addition, the eGFR and the change from baseline in eGFR will be summarized by visit and treatment group.

The FAS will be used for the above analyses.

9.7 Interim analyses

No efficacy interim analysis is planned.

9.8 Sample size calculation

The sample size (2500 randomized patients) has been chosen in order to provide adequate power to evaluate both primary and secondary endpoints.

With an alpha of one-sided 0.0225, the power for the NT-proBNP will range from 92% to more than 99%, to detect a relative reduction ranging from 11% to 24% in change from baseline to Week 12 in NT-proBNP, assuming a standard deviation of 0.81 for change from baseline in the

log-transformed NT-proBNP (based on PARAMOUNT-HF data of patients with baseline KCCQ CSS < 75) and an overall drop-out rate of 10%.

With an alpha of one-sided 0.0025, the power for the 6MWD will range from 90% to 99%, to detect a mean difference ranging from 22 meters to 30 meters in change from baseline to Week 24 in 6MWD, assuming a standard deviation of 120 meters (Ingle et al 2005), an overall drop-out rate of 10%, and an overall proportion of 88% for patients with B6MWD ranging from 100 meters to 450 meters.

With an alpha of one-sided 0.0225, the power for the KCCQ CSS will range from 87% to 99%, to detect a mean difference ranging from 2 points to 3 points in change from baseline to Week 24 in KCCQ CSS, assuming a standard deviation of 15.52 points for change from baseline in the KCCQ CSS (based on PARAMOUNT-HF data of patients with baseline KCCQ CSS < 75) and an overall drop-out rate of 5%.

All alpha levels in the following sample size calculations will be one-sided 0.025.

This sample size of 2500 randomized patients aims to provide a power of approximately 90%, with the one-sided alpha level of 0.025, to demonstrate a 5% responder advantage in at least 5-point deterioration for patients who are treated with LCZ696 over individualized medical therapy when assuming the proportion of patients with at least 5-point deterioration from baseline to Week 24 in the individualized medical therapy group is 20% (based on PARAMOUNT-HF data of patients with baseline KCCQ CSS < 75) and an overall 5% dropouts.

With the same assumption of the dropout rate, this sample size will also provide a power of 69% to detect a 5% responder advantage in at least 5-points improvement in the KCCQ clinical summary score for patients who are treated with LCZ696 over individualized medical therapy when assuming the proportion of patients with at least 5-points improvement from baseline to Week 24 in the individualized medical therapy group is 55% (based on PARAMOUNT-HF data of patients with baseline KCCQ CSS < 75).

The sensitivity of power for at least 5-points deterioration in the KCCQ clinical summary score to changes in assumptions is outlined in Table 9-1.

Table 9-1 Sensitivity of power for at least 5-points deterioration in KCCQ clinical summary score to changes in assumptions for N = 2500

Assumed probability of at least 5-points deterioration			Power for at least 5-points deterioration (one-sided alpha = 0.025)			
Individualized medical therapy	LCZ696	Difference	With 5% drop-out rate	With 10% drop-out rate	With 15% drop-out rate	With 20% drop-out rate
20%	15%	-5%	90%	88%	86%	84%
35%	30%	-5%	74%	72%	69%	67%

The sensitivity of power for at least 5-points improvement in the KCCQ CSS to changes is outlined in Table 9-2.

Table 9-2 Sensitivity of power for at least 5-points improvement in KCCQ clinical summary score to changes in assumptions for N = 2500

Assumed probability of at least 5-points improvement			Power for at least 5-points improvement (one-sided alpha = 0.025)			
Individualized medical therapy	LCZ696	Difference	With 5% drop-out rate	With 10% drop-out rate	With 15% drop-out rate	With 20% drop-out rate
55%	60%	5%	69%	67%	65%	62%
41%	46%	5%	69%	67%	64%	62%

The assumed dropout rates (Table 9-1 and Table 9-2) are for the purpose of power sensitivity analysis. During the conduct of the study, all efforts will be made to reduce missing data.

For other secondary endpoints, this sample size will provide adequate powers for reasonable effect size assumptions: power of 90% for NYHA class change, assuming 14% of the patients in the comparator and 19% of the patients in the LCZ696 group are improved in NYHA class change, 6% of the patients in the comparator and 5% of the patients in the LCZ696 group are worsened in NYHA class change (based on Week 24 PARAMOUNT-HF data of patients with baseline KCCQ CSS < 75); and power of approximately 90% to detect a between treatment group mean difference of 1.4 points or more in change from baseline in SF-36 physical component summary score, assuming a standard deviation of 10-points (Edelmann et al 2013).

East 6.3 was used for the sample size calculations.

10 Ethical considerations

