9.4.2 Statistical model, hypothesis, and method of analysis

Testing strategy

The following primary null hypotheses will be included in the testing strategy.

- H_1 : LCZ696 is no better than the comparator in change from baseline in log(NT-proBNP) at Week 12 in the overall study population
- H_2 : LCZ696 is no better than the comparator in change from baseline in 6MWD at Week 24 in patients with B6MWD ranging from 100 meters to 450 meters.

The following secondary null hypotheses will be included in the testing strategy.

- H_3 : LCZ696 is no better than the comparator in change from baseline in KCCQ CSS at Week 24 in the overall study population.
- H_4 : LCZ696 is no better than the comparator in NYHA change from baseline at Week 24 in the overall study population.

Each null hypothesis is tested against the one-sided alternative that LCZ696 is better than the comparator in the corresponding variable.

In order to control the family-wise type-I error rate at the one-sided 0.025 significance level, a sequentially rejective multiple testing procedure based on the graphical presentation ([Bretz et al 2009](#)) will be employed, whereby H_1 and H_2 will be tested first at initially assigned level of one-sided $(9/10) \times \alpha = 0.0225$ and one-sided $(1/10) \times \alpha = 0.0025$, accordingly. If H_1 and/or H_2 are rejected, the alpha for the rejected null hypotheses will be propagated to H_3 , such that, H_3

[figure not shown]
will be tested at the updated alpha level (one-sided 0.025 if both H_1 and H_2 are rejected; one-sided 0.0225 if H_1 is rejected but H_2 is not rejected; one-sided 0.0025 if H_2 is rejected but H_1 is not rejected); if H_3 is rejected, the alpha will be propagated to H_2 or H_4 based on the initial step rejection status.

- With H_1 rejected but H_2 not rejected at the initial step, if H_3 is rejected at one-sided 0.0225, the alpha will be propagated to H_2 , such that, H_2 will be tested again at one-sided 0.025; if H_2 is rejected at one-sided 0.025, the alpha will be further propagated to H_4 . Otherwise, the testing procedure will stop.
- With H_2 rejected but H_1 not rejected at the initial step, if H_3 is rejected at one-sided 0.0025, the alpha will be propagated to H_4 , such that, H_4 will be tested at one-sided 0.0025. Otherwise, the testing procedure will stop.

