- With both H_1 and H_2 rejected at the initial step, if H_3 is rejected at one-sided 0.025, the alpha will be propagated to H_4 , such that, H_4 will be tested at full alpha (one-sided 0.025). Otherwise, the testing procedure will stop.

Figure 9-1 provides graphical illustration of the sequentially rejective testing procedure.

Figure 9-1 Graphical illustration of the sequentially rejective testing procedure

Based on the above testing procedure, if applicable, H₁, H₂ and H₃ will be tested based on the corresponding MMRM models (Section 9.4.2, Section 9.5.1.1), H₄ will be tested based on the longitudinal proportional cumulative odds model (Section 9.5.1.3)

If statistical significance had been established in the mean difference in change from baseline to Week 24 for KCCQ CSS, the following responders will be analyzed accordingly, based on the longitudinal binary logistic regression models (Section 9.5.1.1), to further illustrate the clinical relevance of the observed differences in terms of proportion of responders.

- KCCQ CSS improvement (defined by at least 5 points improvement);
- KCCQ CSS deterioration (defined by at least 5 points deterioration);

No multiplicity adjustment will be done for these supportive responder analyses (i.e., the tests for the responder analyses will be performed at nominal level of one-sided 0.025).

NT-proBNP analyses

The changes from baseline in log(NT-proBNP) will be analyzed using a mixed model for repeated measures (MMRM), in which, the response variable will be the changes from baseline in log(NT-proBNP); stratum (defined by prior ACEi/ARB medication usage [ACEi, ARB, None]), region, treatment (LCZ696, individualized medical therapy), visit and treatment-by-visit interaction will be included as fixed-effect factors; baseline log(NT-proBNP), stratum-by-baseline and visit-by-baseline interactions will be included as covariates; the within-patient covariance will be modeled using an unstructured covariance matrix (a common matrix for the two treatment groups). The analysis will include all post-baseline scheduled visits up to Week 12 (Week 4, Week 12) and will be performed based on the likelihood method with an assumption of missing at random (MAR) for missing data (Siddiqui et al 2009, National Research Council 2010).

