9.5.1.3 NYHA class change

The NYHA class change is a three-category ordinal variable with levels: “improved”, “unchanged”, and “worsened”, defined by at least one class improvement, no change, at least one class worsening, in NYHA class, respectively. For patients who died, the NYHA class change after the death will be categorized into “worsened”. For patients who permanently discontinue study treatment, values collected after permanent discontinuation will generally be included in the analysis.

The NYHA class change will be analyzed using a longitudinal proportional cumulative odds model, in which, the response variable will be the NYHA class change (order defined by “improved” < “unchanged” < “worsened”); stratum (defined by prior ACEi/ARB medication usage [ACEi, ARB, None]), region, treatment (LCZ696, individualized medical therapy), visit, treatment-by-visit interaction, baseline NYHA class, stratum-by-baseline and visit-by-baseline interactions will be included as fixed-effect factors; BSBP and stratum-by-BSBP interaction will be included as covariates; patient-specific intercepts will be included as random effects. The analysis will include all post-baseline scheduled visits up to Week 24 (Week 2, Week 4, Week 8, Week 12, Week 16, Week 20 and Week 24) and will be performed based on the likelihood method with an assumption of MAR for missing data (other than due to death).

Based on the longitudinal proportional cumulative odds model, the secondary null hypothesis, H_4 , will be tested (if applicable) based on the testing strategy, the estimate and the two-sided 95% confidence interval will be provided for the adjusted odds ratio (LCZ696 over individualized medical therapy) at Week 24.

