- With H2 rejected but H1 not rejected at the initial step, if H3 is rejected at one-sided 0.0025, the alpha will be propagated to H4, such that, H4 will be tested at one-sided 0.0025. Otherwise, the testing procedure will stop.
- With both H1 and H2 rejected at the initial step, if H3 is rejected at one-sided 0.025, the alpha will be propagated to H4, such that, H4 will be tested at full alpha (one-sided 0.025). Otherwise, the testing procedure will stop.

Figure 2-1 provides graphical illustration of the sequentially rejective testing procedure.

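### Is the 90% power for NYHA class change misleading because it ignores the hypotheses that must be rejected before NYHA is tested?

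*Protocol*

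**What the plan says.** Protocol 9.8 takes the two primary hypotheses and KCCQ CSS first, at alphas that come from the testing procedure: one-sided 0.0225 for NT-proBNP (H1), 0.0025 for 6MWD (H2) and 0.0225 for KCCQ CSS (H3). Each has a range of effects; for H3 the text is "to detect a mean difference ranging from 2 points to 3 points in change from baseline to Week 24 in KCCQ CSS". It then announces: "All alpha levels in the following sample size calculations will be one-sided 0.025". Under that statement come the KCCQ responder analyses, NYHA class change with "power of 90% for NYHA class change", and SF-36 PCS. SAP section 3 repeats the text.

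Protocol 9.4.2 and SAP 2.5.2 give the routes to NYHA (H4):

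- H1 and H2 both rejected at the first step: "With both H_1 and H_2 rejected at the initial step, if H_3 is rejected at one-sided 0.025, the alpha will be propagated to H_4", and H4 is tested at the full one-sided 0.025.
- H1 rejected, H2 not: H3 must be rejected, and H2 is then retested; "if H_2 is rejected at one-sided 0.025, the alpha will be further propagated to H_4".
- H2 rejected, H1 not: H3 must be rejected at 0.0025, "such that, H_4 will be tested at one-sided 0.0025".

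In every other case H4 is not tested.

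**The concern.** The alphas for H1 to H3 are taken from the procedure, so a reader may assume that the NYHA figure reflects the procedure as well. It does not: it comes from the NYHA rates alone. H4 may never be tested, or may be tested at a tenth of the alpha, and neither document gives a power that allows for this. The NYHA sentence also names no drop-out rate, although those for H1 to H3 do. If the earlier hypotheses fail often, the chance of a confirmatory NYHA result is below 90%, and the statement that 2500 patients give adequate power for primary and secondary endpoints is too favourable for this one.

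**Working it through.** **Inputs (Protocol 9.8 unless noted).** 2500 patients randomized 1:1 (Protocol 3.1), so 1250 per arm.

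- H1: 11-24% reduction, SD 0.81 on the log scale, 10% drop-out, so 1125 per arm.
- H2: 22-30 m, SD 120 m, 10% drop-out, 88% in the walk-distance subset, so 1125 × 0.88 = 990 per arm.
- H3: 2-3 points, SD 15.52, 5% drop-out, so 1187.5 per arm.
- H4: improved/unchanged/worsened 14/80/6% for comparator and 19/76/5% for LCZ696. Drop-out not stated; 0-10% tried.

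**Step 1: the plan's own figures, H1 to H3.** Power = Φ(μ − z₁₋α), with μ = effect / (SD × √(2/n)). At the lower end:

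- H1: μ = 0.1165 / 0.03415 = 3.41; power 92.0% at 0.0225 (stated 92%).
- H2: μ = 22 / 5.394 = 4.08; power 89.8% at 0.0025 (stated 90%) and 98.3% at the 0.025 retest.
- H3: μ = 2 / 0.6369 = 3.14; power 87.2% at 0.0225 (stated 87%), 88.1% at 0.025 and 63.0% at 0.0025.

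**Step 2: the 90% for NYHA.** For a Wilcoxon test at one visit, the probability that an LCZ696 patient does better, counting ties as half, is

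0.19 × 0.86 + 0.76 × 0.06 + 0.5 × (0.19 × 0.14 + 0.76 × 0.80 + 0.05 × 0.06) = 0.5278.

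The tie correction is 1 − Σp̄³ = 0.5208, where p̄ are the average category proportions, and the variance is (0.5208/12) × (2/n). With n = 1187.5 per arm, μ = 0.0278 / √(0.0434 × 2/1187.5) = 3.25. Power at one-sided 0.025 is 90.2%. It is 91.6% with no drop-out and 88.6% with 10%. The stated 90% is right as a stand-alone power at the announced alpha.

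**Step 3: H4 under the procedure, lower-end effects, independent statistics, stand-alone H4 power set to 90%.** At 0.0025 such a test has power 66.8%.

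| Route | Probability of reaching H4 | × H4 power | Contribution |
|---|---|---|---|
| H1, H2, H3 rejected | 0.920 × 0.898 × 0.881 = 0.728 | 0.900 | 65.6% |
| H1, H3, then H2 on retest | 0.920 × (0.983 − 0.898) × 0.872 = 0.068 | 0.900 | 6.1% |
| H2, H3 rejected, H1 not | (1 − 0.920) × 0.898 × 0.630 = 0.045 | 0.668 | 3.0% |
| Total | 0.841 | | 74.7% |

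**Step 4: correlation.** The documents give no correlation between the four statistics, so a common value was assumed and the procedure simulated (4,000,000 draws per setting, stand-alone H4 power 90%). Probability of rejecting H4:

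| Effects of H1, H2, H3 | 0 | 0.5 | 0.7 | 0.9 |
|---|---|---|---|---|
| Lower end (11%, 22 m, 2 points) | 74.7% | 78.4% | 81.0% | 84.7% |
| Mid-range (17.5%, 26 m, 2.5 points) | 87.6% | 88.6% | 89.2% | 89.9% |
| Upper end (24%, 30 m, 3 points) | 89.7% | 89.9% | 90.0% | 90.0% |

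**Step 5: which effect drives the loss.** With one effect at its lower end, the other two mid-range, correlation 0-0.7 and 5% NYHA drop-out, H4 power is 79-83% for KCCQ, 85-87% for NT-proBNP and 86-89% for 6MWD. The clear loss comes mainly from KCCQ at 2 points.

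**The case for a change.** The best case for a change is this. The lower-end effects are the protocol's own; they produce its quoted 92%, 90% and 87%. If all three hold, H4 goes untested in roughly 14-16% of trials, and a better NYHA model cannot alter that share because it depends on H1 to H3 alone. KCCQ at 2 points is enough on its own to bring H4 down to about 79-83%. Announcing 0.025 does not tell the reader that H4 may be skipped or tested at 0.0025.

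All of that is arithmetically sound. Three things limit its weight.

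- NYHA is not treated differently from the rest of the section. The KCCQ figure at 0.0225 is equally stand-alone, since it ignores the chance that H1 fails. And 0.025 is the alpha H4 receives on both routes that require H1, H2 and H3 to be rejected; the 0.0025 route supplies only 3.0 of the 74.7 points.
- The 75-81% needs three effects at their minimum together while NYHA keeps its single stated value. That value comes from PARAMOUNT-HF, where Protocol 1.1 reports a 23% greater NT-proBNP reduction against valsartan, close to the top of the 11-24% range.
- The calculation is approximate. H1 to H3 will be tested by MMRM with baseline covariates, and for H4 "The NYHA class change will be analyzed using a longitudinal proportional cumulative odds model". If covariate adjustment cut the standard deviations of H1 to H3 by 5% or 10% (an assumption), lower-end H4 power would be about 79-84% or 83-86% at correlation 0-0.7.

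What stands is a point of presentation: the sentence does not call the 90% marginal and omits the drop-out rate.

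**Conclusion.** The concern describes the figure correctly but does not show an error. The 90% is the marginal power of H4 at an alpha the section states, it reproduces, and nowhere is it called the power under the full procedure. A reader can see every condition for testing H4 in Protocol 9.4.2 and SAP 2.5.2.

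The gap between marginal and procedure-based power is at most about 2 points at mid-range effects and negligible at the upper end. It reaches about 5-15 points only if all three earlier effects are at their minimum (75-85% for correlation 0-0.9). These figures rest on assumed correlations, an assumed NYHA drop-out and single-visit two-sample approximations, so they should not be inserted as the design's power.

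Reporting procedure-based power would alter no test, alpha level, sample size, estimate or conclusion. The sponsor may call the 90% marginal and name the drop-out used if the section is revised for other reasons, but the plan does not need it.
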